## **SAfety and Effectiveness of the Treatment of Wide Neck, Saccular Intracranial Aneurysms with the Neuroform Atlas™ Stent System**

### **Short Study Name: ATLAS**

#### **3.8.3 Treatment of Previously Treated Aneurysms**

Target aneurysms that have previously been treated with embolic coiling can be treated under this Study Protocol, assuming that the subjects involved meet all of the study inclusion/exclusion criteria as outlined in **Section 2.6, Study Population and Source of Subjects**. Subjects who have had previous stent-assisted coiling of the target aneurysm are not eligible for inclusion in this study.

#### **3.8.4 Implant of More than One Stent**

Up to two stents may be deployed in the treatment of a given aneurysm, but both stents must be Neuroform Atlas™ Stents. The use of other intracranial stents for treatment of the target aneurysm is not allowed in this study.

### **3.9 Post-Implant**

#### **3.9.1 Post-Implant Pharmacotherapy**

A standard antiplatelet regimen is required for post-implant use in enrolled subjects with unruptured intracranial aneurysms in accordance with routine clinical practice, unless it becomes contraindicated in an individual subject due to a medical condition. Substitutions for these medications are allowed at the discretion of the Investigator as long as the antiplatelet efficacies are equivalent.

##### **Recommended Dosage and Required/Recommended Duration:**

- ASA 75 or 81 mg (minimum dose) to 325 mg (maximum dose) PO q.d., required for at least 3 months after the implant procedure; recommended for life
- Clopidogrel/Plavix 75 mg PO q.d., required for at least 3 months after the implant procedure

#### **3.9.2 Post-Implant Assessments**

At the Investigator's discretion, a treated subject may be discharged from the hospital when he/she is clinically stable. Prior to discharge and within 72 hours of the procedure, the following assessments and/or procedures will be performed on all treated subjects:

- Neurologic rating/grading scales including the following:
  - mRS (all subjects)
  - Hunt and Hess (for subjects who previously had a ruptured aneurysm and evidence of subarachnoid hemorrhage)
- Assessment and documentation of any adverse events arising after the procedure but prior to discharge.

At the time of discharge, designated staff at the clinical site will review the study requirements with the subject in order to maximize compliance with the follow-up schedule and the post-implant medication regimen. The staff will instruct the subject to return for follow-up assessments in accordance with the study event schedule outlined in **Table 2**, and if possible, they will establish and schedule a date for the first follow-up visit and/or procedure. In addition, the staff will instruct the subject to take the recommended antiplatelet medication, and will ask the subject to check in with the clinical site prior to discontinuing any antiplatelet medication in the absence of an emergency.

### **3.10 Follow Up Visits**

Enrolled and treated subjects will return for follow-up visits and collection of primary and/or secondary endpoint data as required at two, six, and twelve months. Long-term outcomes data will be collected at

# **SAfety and Effectiveness of the Treatment of Wide Neck, Saccular Intracranial Aneurysms with the Neuroform Atlas™ Stent System**

## **Short Study Name: ATLAS**

two and three years post-implant. During these follow-up visits, assessments and/or procedures will be performed as follows:

### **Two Months (60 days) ± 1 Month Post-Implant:**

- Neurological rating/grading scales including the following:
  - mRS (all subjects)
  - NIHSS (only if mRS score is > 0 in association with an adverse neurological event)
- Angiography (MRA or DSA) - only if required per site standard of care
- Assessment and documentation of any adverse events arising since discharge
- Assessment of compliance to the antiplatelet regimen

### **Six Months (180d) ± 1 Month Post-Implant:**

- Neurologic rating/grading scales including the following:
  - mRS (all subjects)
  - NIHSS (only if mRS score is > 0 in association with an adverse neurological event)
- Angiography (MRA or DSA) - only if required per site standard of care
- Assessment and documentation of any adverse events arising since the previous follow-up visit
- Assessment of compliance to the antiplatelet regimen

### **Twelve Months (365d) ± 2 Months Post-Implant:**

- Neurological examination (including global neurological assessments and evaluation for cranial nerve deficits)
- Neurologic rating/grading scales including the following:
  - mRS (all subjects)
  - NIHSS (all subjects)
  - Hunt and Hess (for subjects who previously had a ruptured aneurysm and evidence of subarachnoid hemorrhage)
- Angiography (DSA)

*NOTE: 12-month angiography (DSA) is used to assess the primary endpoint and is required for all subjects*

- Assessment and documentation of any adverse events arising since the previous follow-up visit
- Assessment of compliance to the antiplatelet regimen
- Quality of Life assessment

### **Two Years (730d) ± 6 Months Post-Implant:**

- Neurological examination (including global neurological assessments and evaluation for cranial nerve deficits, if applicable)
- mRS assessment
- Radiological imaging (MRA, DSA or CTA), if performed per institutional standard of care
- Assessment and documentation of any adverse events arising since the previous follow-up visit, including all new and ongoing adverse events

# **SAfety and Effectiveness of the Treatment of Wide Neck, Saccular Intracranial Aneurysms with the Neuroform Atlas™ Stent System**

## **Short Study Name: ATLAS**

- Assessment of antiplatelet regimen
- Retreatment assessment

### **Three Years (1095d) ± 6 Months Post-Implant:**

- Neurological examination (including global neurological assessments and evaluation for cranial nerve deficits, if applicable)
- mRS assessment
- Radiological imaging (MRA, DSA or CTA), if performed per institutional standard of care
- Assessment and documentation of any adverse events arising since the previous follow-up visit, including all new and ongoing adverse events
- Assessment of antiplatelet regimen
- Retreatment assessment

*NOTE: Two- and 3-year office visits with neurological examination are required. If the 3-year visit window has elapsed at the initiation of the PAS, subjects will be asked to return for at least 1 follow-up visit. In the event a subject refuses to return for an office visit, effort should be made to conduct telephone follow-up to complete an adverse event assessment and obtain mRS scores.*

### **3.11 Unscheduled Visits**

Imaging performed in response to an adverse event will be documented in the case report forms. These images will be shared with the Imaging Core Lab, and copies of the images will be provided to the Sponsor so that CEC review and event adjudication can be facilitated. If a subject is suspected of having a stroke, it is recommended that an imaging study be performed within 24 hours of the onset of symptoms in order to confirm, and to evaluate whether the stroke is/was ischemic or hemorrhagic in nature. In addition, a neurological examination and/or an assessment using neurologic rating/grading scales (mRS, NIHSS, Hunt and Hess) should be performed as required in order to determine the severity of the stroke.

If a subject presents with an adverse event, he/she will receive appropriate treatment per site standard of care. If the subject's condition precludes him/her from undergoing angiography or any other evaluation specified in the protocol, the Investigator should document whether a stable clinical endpoint has been reached, or whether the subject's status is associated with an adverse event possibly related to the device or procedure. All efforts will be made to retain the subject for safety follow up. If the subject is withdrawn from the study, reasons for the subject's inability to continue with study evaluations will be documented.

## **4 Statistical Methods and Considerations**

### **4.1 Trial Success/Failure Criteria**

This is a single arm trial of the Neuroform Atlas™ Stent System in subjects with wide neck aneurysms who will receive stent-assisted coiling with any approved bare metal embolic coils. Up to 360 subjects with wide neck saccular aneurysms who meet all eligibility criteria will be enrolled. The primary effectiveness endpoint is complete occlusion of the targeted lesion at 12 months, and the related study success criterion is to demonstrate that the lower bound of the 95% exact CI observed rate of complete occlusion at 12 months is greater than 50% in both the anterior and posterior circulation cohorts. The primary safety endpoint is any major ipsilateral stroke or neurological death within 12 months, and the

# **Safety and Effectiveness of the Treatment of Wide Neck, Saccular Intracranial Aneurysms with the Neuroform Atlas™ Stent System**

## **Short Study Name: ATLAS**

related study success criteria are to demonstrate that the rate of primary safety events is less than 20% in the anterior circulation cohort, and less than 25% in the posterior circulation cohort.

### **4.2 Sample Size Estimate and Justification**

#### Anterior Circulation Cohort:

A sample size of up to 180 subjects with intracranial aneurysms in the distal anterior circulation has been selected for this study in order to provide 153 evaluable subjects at 12 months, with an estimated 15% attrition rate. Assuming an effectiveness primary endpoint response rate of 62% (per the findings of a meta-analysis of Neuroform stent literature as performed by King et al), the expected lower bound of the exact binomial two-sided 95% confidence interval around the success rate is greater than 50%. Assuming a safety primary endpoint rate of 8%, the expected upper bound of the exact binomial two-sided 95% confidence interval around the success rate is less than 20%. A sample size of 153 evaluable subjects provides 85% power to demonstrate the effectiveness endpoint, and a power of approximately 99% to successfully demonstrate the safety endpoint given the observed rates stated above. The combined probability of the two endpoints is  $(.85) \times (.99) = .842$ .

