## **SAfety and Effectiveness of the Treatment of Wide Neck, Saccular Intracranial Aneurysms with the Neuroform Atlas™ Stent System**

### **Short Study Name: ATLAS**

subsequently received approval via Premarket Approval (PMA) application for use with embolic coils in the treatment of wide-neck saccular intracranial aneurysms in the anterior circulation (P180031; May 2019).

Since the original approval, stent assisted coiling using the Neuroform Stent System has been the subject of numerous scientific articles. In a meta-analysis of the published literature on the Neuroform Stent System, King et al reported that complete occlusion rates on final follow-up averaged 61.1% overall in 2,111 aneurysms treated during a 10 year period (2004 to 2014). In the treatment of wide neck aneurysms, this represents a substantial improvement in outcomes compared to embolic coiling alone.

Since the Neuroform Microdelivery System market introduction in the US, there have been a number of SAC devices approved by FDA via HDE such as the Codman Enterprise Vascular Reconstruction Device, MicroVention's LVIS device, Pulsar Vascular's PulseRider Aneurysm Neck Reconstruction Device, and Stryker Neurovascular's Neuroform Atlas Stent System. In May 2018, MicroVention's LVIS and LVIS Jr. coil assist stents received PMA approval (P170013). In May 2019, Stryker Neurovascular's Neuroform Atlas Stent System received PMA approval for use in the anterior circulation.

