Analyses for both cohorts will be performed by constructing two-sided 95% confidence intervals about the estimates of the percentage of subjects with complete aneurysm occlusion and the percentage of subjects experiencing a major ipsilateral stroke or neurological death using the exact binomial (Clopper-Pearson) method. For the effectiveness endpoint of total occlusion, the lower bound of this confidence interval will be compared to 50% for both the anterior and posterior circulation cohorts. For the safety endpoint of major ipsilateral stroke and neurological death, the upper bound of the confidence interval will be compared to 20% for the anterior circulation cohort, and 25% for the posterior circulation cohort.

Success requires safety and effectiveness endpoints to be met in each cohort separately. Success in the anterior cohort occurs when the lower bound of the effectiveness endpoint is above 50% and the upper bound of the safety endpoint is below 20%. Success in the posterior cohort occurs when the lower bound of the effectiveness endpoint is above 50% and the upper bound of the safety endpoint is below 25%.

The analysis of long-term safety and effectiveness data will be descriptive only, as no formal hypotheses will be tested based on data collected during this phase of the study. Survival analysis will be used to estimate the incidence of specified safety endpoint events, as well as retreatment of the target aneurysm. Details regarding the survival analyses are summarized in **Table 7**.

**Safety and Effectiveness of the Treatment of Wide Neck, Saccular Intracranial Aneurysms with the Neuroform Atlas™ Stent System**

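### The 85% effectiveness power is not what the planned exact test delivers: at 153 evaluable subjects it is 81.4% at 62%, and 74.7% at the 61.1% that the protocol reports from the same source

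*Combined protocol and SAP*

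**What the plan says.** Section 4.2 plans up to 180 anterior-circulation subjects "in order to provide 153 evaluable subjects at 12 months, with an estimated 15% attrition rate". The planning rate is introduced with "Assuming an effectiveness primary endpoint response rate of 62% (per the findings of a meta-analysis of Neuroform stent literature", and the power statement is "A sample size of 153 evaluable subjects provides 85% power to demonstrate the effectiveness endpoint". The section then multiplies .85 by a safety power of .99 to reach a combined .842.

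For the posterior cohort, section 4.2 says the same effectiveness power applies at 153 evaluable subjects. The synopsis gives the 85% and the .842 for both cohorts.

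The success rule is exact. Section 4.1 requires that "the lower bound of the 95% exact CI observed rate of complete occlusion at 12 months is greater than 50" percent. Section 4.6 describes "constructing two-sided 95% confidence intervals about the estimates of the percentage of subjects with complete aneurysm occlusion", formed "using the exact binomial (Clopper-Pearson) method". Section 4.4 also specifies the exact binomial distribution.

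On the source of the planning rate, section 1.1 says of the same reference (59) that "complete occlusion rates on final follow-up averaged 61.1% overall in 2,111 aneurysms".

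**The concern.** Two things do not fit together.

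- Section 4.2 describes an exact binomial criterion, but the power beside it looks like the output of a large-sample formula. An exact interval is conservative, so its power at a given n is usually lower than the approximation suggests.
- The 62% is credited to a reference for which the protocol elsewhere reports 61.1%. Rounding does not turn 61.1% into 62%, and no other derivation is given. The 61.1% is complete occlusion alone, while the primary endpoint (section 2.4.1.1) also requires no retreatment and no parent artery stenosis above 50%.

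Effectiveness is the endpoint that limits the trial, because safety power is close to 99%. An error here passes almost unchanged into the joint probability of success, which is stated for both cohorts.

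**Working it through.** **Inputs.** n = 153 evaluable (section 4.2; 180 × 0.85 = 153). Performance goal 50%, two-sided 95% Clopper-Pearson lower limit (sections 4.1, 4.4, 4.6), so 0.025 in the tested direction. True rate 62% (section 4.2) or 61.1% (section 1.1). Safety: 8% true against a 20% limit (anterior) and 12% against 25% (posterior), section 4.2.

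**1. Reproducing the stated 85%.** One-sample normal approximation, with the null variance for the cutoff and the alternative variance for the power:

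Power = Φ{[(p1 − p0) − 1.96·√(p0(1 − p0)/n)] / √(p1(1 − p1)/n)}

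- √(0.25/153) = 0.04042 and √(0.62 × 0.38/153) = 0.03924
- (0.12 − 1.96 × 0.04042)/0.03924 = 1.039, and Φ(1.039) = 85.06%

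An arcsine calculation gives 85.0%. The null variance used throughout gives 84.3%. The first two match the stated figure.

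**2. The exact rule at n = 153.**

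| Successes | Clopper-Pearson 95% lower limit | Criterion met? |
|---|---|---|
| 89 (58.2%) | 49.93% | No |
| 90 (58.8%) | 50.59% | Yes |

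Success therefore needs X ≥ 90. The attained one-sided type I error is P(X ≥ 90 | 50%) = 1.76%. A cutoff of 89 would give 85.5% power, but it fails the plan's own rule and has a type I error of 2.60%.

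**3. Exact power, P(X ≥ 90), n = 153.**

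| True rate | Exact power | Chance of missing |
|---|---|---|
| 62% | 81.4% | 18.6% |
| 61.1% | 74.7% | 25.3% |
| 60% | 65.0% | 35.0% |
| 58% | 45.2% | 54.8% |

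A true rate of about 62.6% is needed for 85% power at this n.

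**4. Joint probability, by the plan's own product rule.** Anterior safety succeeds with 20 or fewer events: P(X ≤ 20 | 8%) = 98.9%. Posterior safety succeeds with 27 or fewer: P(X ≤ 27 | 12%) = 98.5%. The stated safety power of about 99% is therefore sound.

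| Cohort (fixed n = 153) | At 62% | At 61.1% | Stated |
|---|---|---|---|
| Anterior | .814 × .989 = .806 | .747 × .989 = .739 | .842 |
| Posterior | .814 × .985 = .802 | .747 × .985 = .735 | .842 |

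**5. Is this a quirk of n = 153?** Exact power rises and falls with n, and 153 is a local low. At 62%:

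| n | 152 | 153 | 154 | 155 | 156 | 157 | 158 |
|---|---|---|---|---|---|---|---|
| Power | 83.1% | 81.4% | 84.0% | 82.3% | 84.8% | 83.2% | 85.5% |

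No n from 140 to 157 reaches 85%. It is first reached at 158, is lost again at some larger n (84.0% at 159 and at 164), and holds from 167 on. At 61.1% the corresponding sizes are 184 and 195. If the evaluable number is treated as Binomial(180, 0.85) rather than fixed at 153, average exact power is 83.0% at 62% and 76.5% at 61.1%.

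**The case against.** The strongest reply has five parts.

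- **Discreteness exaggerates the gap.** This stands in part. 153 is only an expected count, and averaging over a binomial evaluable number brings the shortfall at 62% down to 2.0 points (85 − 83.0). It does not close it, and the plan states its power for 153.
- **The primary analysis is on the modified intent-to-treat population with multiple imputation** (sections 4.3 and 4.4), so the analysed number could approach 180. With complete data on all 180, exact power would be 89.3% at 62% and 83.9% at 61.1%. That is an upper limit, because imputed outcomes do not carry full information, and even then power at 61.1% is below 85%.
- **Most of the ten-point gap comes from the rate, not the arithmetic.** Correct: 3.6 points come from the exact test (85 − 81.4) and 6.7 from moving to 61.1% (81.4 − 74.7). The 61.1% is an overall average at final follow-up, and 62% might be another figure in the cited paper. The documents do not say so, so the mismatch has to be reconciled or sourced.
- **The composite rate could go either way.** Within one set of subjects, adding failure conditions cannot raise the rate. But the documents do not say how the source counted retreated aneurysms, and a newer device or the exclusion of planned neck remnants could offset the loss. The size of the effect is therefore unknown, which is a reason to show a range.
- **The posterior cohort is adaptive.** The fixed-n figures above are not its operating characteristics. They correct the plan's own fixed-n statement for that cohort and nothing more.

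It is also fair to say that anterior approval was granted in May 2019, so restating this figure changes no decision there.

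**Conclusion.** The concern holds. Under the test the plan specifies, effectiveness power at 153 evaluable subjects is 81.4% at 62%, not 85%, and 74.7% at the 61.1% reported in section 1.1. The joint probability is about .81 or .74, against .842. If the true composite rate were 61.1%, the chance of missing the effectiveness criterion would be about 25%, against the 15% implied.

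These figures assume complete data on exactly 153 subjects and, for the joint values, the plan's multiplication of the two powers. That the 85% came from a normal approximation is an inference from the match at 85.06%; the exact results do not depend on it. The success criterion and type I error control (1.76% one-sided) are not in question. This is an overstated planning figure that should be corrected.

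**What to change.** In section 4.2 and the synopsis, for both cohorts:

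1. Replace the 85% with exact Clopper-Pearson power at n = 153: 81% at 62% and 75% at 61.1%. Name the method.
2. Replace .842 with about .81 at 62% and .74 at 61.1%. In the posterior cohort (.80 and .74), label these as fixed-sample values that do not describe the adaptive design.
3. Either use 61.1% as the planning rate, in line with section 1.1, or cite where 62% comes from.
4. State that the source rate is complete occlusion alone, and show power for a composite rate a few points lower (65.0% at 60%, 45.2% at 58%).

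The cost is wording and a less favourable stated power. The sample size, success rule and analysis stay as they are.

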#### Posterior Circulation Cohort:

Separate analyses of these cohort data will be performed to support an indication for use in the posterior circulation.

A sample size of up to 180 subjects with intracranial aneurysms in the posterior circulation (including vertebral, basilar and posterior cerebral arteries) will also be enrolled in order to provide 153 evaluable subjects at 12 months, with an estimated 15% attrition rate. While the safety endpoint rate for posterior circulation subjects may be higher than that for the anterior circulation subjects, that rate is not expected to exceed 12%. Assuming a safety primary endpoint rate of 12%, the expected upper bound of the exact binomial two-sided 95% confidence interval around the success rate is less than 25%. A sample size of 153 evaluable subjects provides a power of approximately 99% to successfully demonstrate the safety endpoint given the observed rates stated above. Based on outcomes in the MAPS study, the effectiveness rate for posterior circulation subjects is expected to be very close to that of anterior circulation subjects. Therefore, the statement of power to demonstrate effectiveness for a sample size of 153 evaluable anterior circulation subjects also holds for a sample size of 153 evaluable posterior circulation subjects.

For the posterior circulation cohort, a Bayesian adaptive study design (“Goldilocks” approach) providing for interim analyses of accumulated data will be used to select the final sample-size. The first interim data analysis will occur once 100 posterior circulation subjects have been enrolled. Based on enrollment rates and the frequency of disease in the posterior circulation, at the time this interim analysis is performed it is estimated that primary endpoint data will be available for approximately 39 – 63 posterior circulation subjects. If, at an interim analysis, there is at least a 95% predictive probability of observing a true rate of complete occlusion that is higher than 50%, enrollment in the posterior circulation cohort will be stopped early for success. The maximum sample-size for the posterior circulation cohort will be no more than 180 subjects.

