# **Safety and Effectiveness of the Treatment of Wide Neck, Saccular Intracranial Aneurysms with the Neuroform Atlas™ Stent System**

## **Short Study Name: ATLAS**

	
rate is greater than 50%. Assuming a safety primary endpoint rate in the posterior circulation of 12%, the expected upper bound of the exact binomial two-sided 95% confidence interval around the success rate is less than 25%.
 
A sample size of 153 evaluable subjects provides 85% power to demonstrate the effectiveness endpoint, and a power of approximately 99% to successfully demonstrate the safety endpoint given the observed rates stated above. The combined probability of the two endpoints is <math>(.85) \times (.99) = .842</math>.
 
For the posterior circulation cohort, a Bayesian adaptive study design (“Goldilocks” approach) providing for interim analyses of accumulated data will be used to select the final sample-size. The first interim data analysis will occur once 100 posterior circulation subjects have been enrolled. Based on enrollment rates and the frequency of disease in the posterior circulation, at the time this interim analysis is performed it is estimated that primary endpoint data will be available for approximately 39 – 63 posterior circulation subjects. If, at an interim analysis, there is at least a 95% predictive probability of observing a true rate of complete occlusion that is higher than 50%, enrollment in the posterior circulation cohort will be stopped early for success. The maximum sample-size for the posterior circulation cohort will be no more than 180 subjects.

Planned Number of Sites:	Up to 40 sites will participate in the clinical study.
Randomization:	This study is a non-randomized, open label, single-arm study.

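### The posterior cohort's stated powers (85%, about 99%, .842) hold only at its 153-evaluable maximum; none is given for the adaptive design that sets its size

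*Combined protocol and SAP*

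**What the plan says.** Section 4.2, posterior cohort, gives the safety power at one sample size: "A sample size of 153 evaluable subjects provides a power of approximately 99% to successfully demonstrate the safety endpoint". The input is a 12% event rate, and the section expects an upper limit under 25%: "Assuming a safety primary endpoint rate of 12%, the expected upper bound of the exact binomial two-sided 95% confidence interval around the success rate". For effectiveness, the section argues that the posterior rate should be close to the anterior one and carries over the anterior power at 153 evaluable, which is 85% ("Assuming an effectiveness primary endpoint response rate of 62"%). The synopsis prints 85% and about 99% for the posterior cohort and multiplies them: "The combined probability of the two endpoints is" .842. Section 4.2 prints that product for the anterior cohort only.

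Both places then say that a Bayesian adaptive (Goldilocks) design will choose the posterior cohort's final size, with 180 enrolled as the ceiling. "The first interim data analysis will occur once 100 posterior circulation subjects have been enrolled", when 39 to 63 subjects are expected to have endpoint data. Enrolment stops for success if a 95% predictive probability criterion on complete occlusion is met. The criterion has no safety term.

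Section 4.6 fixes the final tests. "Analyses for both cohorts will be performed by constructing two-sided 95% confidence intervals", and the limits are to be found "using the exact binomial (Clopper-Pearson) method". Both endpoints must pass, with 25% as the limit for safety: "Success in the posterior cohort occurs when the lower bound of the effectiveness endpoint is above 50% and the upper bound of the safety endpoint".

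**The concern.** The 153 evaluable subjects are the ceiling of an adaptive design, not its planned size. A cohort that stops at the first look has about 85 evaluable subjects for the safety test. That stop is triggered by good occlusion results, with no check that the safety test can still pass at the smaller size.

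The documents give no power, expected sample size or simulation for the adaptive design, so a reader has only the ceiling figures. The sponsor and regulator could then take the safety endpoint as almost certain to pass at a 12% event rate, and the cohort as having an 84% chance of success, when neither figure describes the design to be run.

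**Working it through.** **Inputs from the documents.** Occlusion 62% against a goal of 50%; safety events 12% against a goal of 25%; two-sided 95% Clopper-Pearson intervals; 15% attrition, so 180 × 0.85 = 153 and 100 × 0.85 = 85; first look at 100 enrolled with 39–63 completers; stopping threshold 95%.

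**Step 1: reproduce the stated figures at 153.** The one-sample normal approximation is

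power = Φ[(|p1 − p0|·√n − 1.96·√(p0(1 − p0))) / √(p1(1 − p1))].

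- Effectiveness: (0.12 × 12.369 − 1.96 × 0.5) / 0.4854 = 1.039, so power is 85.1%.
- Safety: (0.13 × 12.369 − 1.96 × 0.4330) / 0.3250 = 2.337, so power is 99.0%.
- Product: 0.851 × 0.990 = .842.

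All three printed figures reproduce.

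**Step 2: the same size with the planned exact tests.**

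- Effectiveness passes at 90 or more of 153: P(X ≥ 90 | 153, 0.62) = 81.4%.
- Safety passes at 27 or fewer of 153: P(X ≤ 27 | 153, 0.12) = 98.5%.
- Product: 0.814 × 0.985 = .802.

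Moving from the normal approximation to the exact tests therefore costs .842 − .802 = 4 joint points before any adaptation.

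**Step 3: the size after a first-look stop.** At 85 evaluable, safety passes at 13 or fewer events: P(X ≤ 13 | 85, 0.12) = 86.4%. This is conditional on stopping there. If all 100 enrolled are analysed, the limit is 16 events and the power 91.3%.

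**Step 4: the whole adaptive design.** Simulation, 60,000 trials per setting. Assumptions that the plan does not supply: a flat Beta(1,1) prior; endpoints independent (as in the plan's own product); either one look at 100 enrolled or looks at 100, 120, 140 and 160. Two readings of the stopping rule were run:

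- *Predictive*: at least 95% predictive probability of passing the final exact effectiveness test at the current enrolment.
- *Posterior*: at least 95% posterior probability that the true occlusion rate exceeds 50%.

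| Analysed | Reading | Stop at first look | Effectiveness | Safety | Joint |
|---|---|---|---|---|---|
| 85% of enrolled | Predictive | 13–19% | about 81% | 94–97% | .76–.78 |
| 85% of enrolled | Posterior | 46–56% | 70–75% | 90–93% | .62–.69 |
| All enrolled | Predictive | 13–21% | 88–89% | 97–98.5% | .86–.87 |
| All enrolled | Posterior | 46–56% | 79–84% | 94–95% | .74–.80 |

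**Step 5: the cost of early stopping alone**, on the plan's 85% evaluable basis, against .802:

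- Predictive: .802 − .78 to .802 − .76, about 2 to 4 joint points.
- Posterior: .802 − .69 to .802 − .62, about 11 to 18 joint points.

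**Step 6: false success.** With occlusion set to 50%, or the safety rate to 25%, the matching final test passed in about 2.5% of simulated trials or fewer. The largest value was 2.6%, for the effectiveness test taken alone under the posterior reading with four looks.

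**The case against.** The plan attaches every figure to 153 evaluable subjects and calls 180 enrolled the maximum. At that size the arithmetic is right, and nothing claims that 99% or .842 survives an early stop. This stands: what is missing is a statement of the adaptive design's operating characteristics. A reader might infer that the 99% is a miscalculation, and the documents do not support that.

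A reader might also take 86.4% as the cohort's safety power. It applies only to trials that stop at 100 enrolled. Under the predictive reading these are 13–19% of trials, and the mean evaluable number is about 126–144.

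A third tempting reading is that joint power is overstated by up to 22 points (.842 against .62). That range includes the 4-point normal-versus-exact gap and depends on the posterior reading. The plan uses the term predictive probability within a named Goldilocks design, but applies it to the true rate exceeding 50%, so the rule is ambiguous and the larger loss is not established.

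The analysis set matters too. Section 4.4 makes all successfully implanted subjects the primary population, and section 4.3 imputes missing endpoints, so the number analysed may exceed 85% of those enrolled. Counting everyone is an optimistic bound, since it ignores imputation variance. Under the predictive reading it gives .86–.87, above .842. The claim that .842 is too high is therefore not robust to the analysis set. The plan's own .842 does rest on evaluable subjects, so the 85% basis is the like-for-like comparison.

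Finally, the simulations give no ground for alleging that control of false success is lost.

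**Conclusion.** The point holds as a gap in the stated design power. The figures 85%, about 99% and .842 describe only a posterior cohort that runs to 153 evaluable, and the documents give no power for the adaptive design that will choose its size.

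On the plan's evaluable basis, both safety and joint power fall below the stated values in every setting examined. Under the predictive reading the loss is moderate: safety is 2–5 points below 99%, and joint power is 6–8 points below .842, of which about half is normal versus exact. Under the posterior reading it is larger. If all enrolled subjects are analysed, safety power is still below 99%, but joint power falls below .842 only under the posterior reading.

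The ranges rest on the assumed flat prior, look schedule and independence of endpoints. The ceiling-only status of the printed figures does not depend on those assumptions.

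**What to change.** In the synopsis (85%, about 99% and .842) and in section 4.2 (about 99% and the carried-over 85%), state that these posterior-cohort figures apply to the maximum of 153 evaluable only.

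Then state, as the posterior cohort's design power, the simulated effectiveness, safety and joint power of the adaptive design at 62% and 12%. Use its actual prior, look schedule, stopping criterion and analysis set, with the exact final tests. Add the safety power at the first-look size (86.4% if 85 are analysed) and at each later look that is actually planned.

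The cost is a short simulation and revised wording. The stated powers may become less favourable. No extra patients and no change to study procedures are needed.
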